### **2.2.1 Randomization and drug dispensing irregularities**

Randomization and drug-dispensing irregularities occur whenever:

1. A randomization is not in accordance with the protocol-defined randomization method, such as a) an ineligible patient is randomized, b) a patient is randomized twice.  
  
OR
2. A patient is given a study drug not allocated by the protocol-defined randomization, such as a) a patient at any time in the study is given a different treatment than as randomized (eg, patients randomized to placebo treatment group received olipudase alfa), or b) a nonrandomized patient is treated with study drug.  
  
OR
3. A patient receives an incorrect dose of olipudase alfa (not matching what the investigator requested, or not matching what IXRS instructed pharmacist to prepare, or infusion prepared for 1 patient given to another patient).

All randomization and drug-dispensing irregularities will be documented in the clinical study report. Whether any of these constitute a major or critical protocol deviation, and whether any of these adversely impact efficacy, is deferred to the decision by the sponsor's clinical team before the database lock in PAP. Nonrandomized, treated patients, if any, will be described separately.

Randomization and drug-dispensing irregularities to be prospectively identified include but are not limited to:

---

**Randomization and drug allocation irregularities**

---

Study drug given without IRT transaction

Erroneous study drug administration

Randomization by error

Patient randomized twice

---

## 2.2.2 Protocol deviations

Protocol deviations are qualitative and quantitative in nature. Qualitative deviations are evaluated and reported in a list by study monitoring team and reviewed by the study team. Quantitative deviations are programmed in SAS from the data, and reviewed by the study team. In both cases, the study team determines whether a deviation is minor, major or critical before the unblinding in PAP (and any that occurs in ETP at the end of study before the database lock). A summary table and a data listing of major or critical deviations will be provided, including, but not limited to, prohibited medication use as well as non-compliance.

## 2.3 ANALYSIS POPULATIONS

Patients treated without being randomized will not be considered randomized and will not be included in any efficacy analysis. Patients who are dispensed study drug without calling the IRT or before calling the IRT are considered nonrandomized patients. They are excluded from any population for analysis, including safety. However, if these patients experienced any significant safety event, they will be documented separately in the clinical study report.

For any patient screened more than once, only the data associated with the second screening will be used in any analysis population. The safety experience associated with any later randomization will be assessed separately.

The **randomized population** includes any patient who had been allocated to a randomized treatment arm by IRT regardless of whether study drug was administered.

### 2.3.1 Efficacy populations

#### 2.3.1.1 Modified intent-to-treat population

The **modified intent-to-treat (mITT) population** is a subset of the randomized population and will include randomized patients who received at least 1 infusion (partial or total). [Note that the design of the study requires patients to be hospitalized for infusion, and the randomization happens when the patient is hospitalized; therefore, it is unlikely that mITT population will differ from the traditional ITT population which constitutes of all randomized patients irrespective of whether one receives a dose of study drug.] Patients will be analyzed in the treatment group to which they are randomized.

### **2.3.1.2 Per-protocol population**

The **per-protocol population** is a subset of the mITT population that has no critical or major protocol deviations that are expected to interfere (the list to be finalized before the database lock and unblinding in PAP) with assessments of the primary efficacy endpoints.

### **2.3.1.3 Other efficacy population**

The **mITT-C population** is the subset of mITT population which excludes patients who had exposure to [REDACTED] of olipudase alfa in the active treatment arm.

### **2.3.2 Safety population**

The **safety population** is defined as a subset of the randomized population who received at least 1 infusion (partial or total), analyzed according to the treatment actually received during the PAP, irrespective of the treatment to which the patient has been randomized. For example, if a placebo patient was rescued to receive olipudase alfa in PAP, this patient will be counted as olipudase alfa treated patient. The safety population will not be changed after patients enter the ETP. Olipudase alfa infusions require special vials to be mixed with the vehicle while placebo infusions do not require these vials, and these vial numbers are called off by IXRS, it is unlikely that there will be any error in treatment received.

The **rescue population** is defined as patients who have used rescue strategy in PAP (ie, unblinded for treatment and continued on olipudase alfa irrespective of the randomized treatment assignment). Data after rescue in PAP will be provided separately for the rescue population.

In addition, nonrandomized but treated patients will not be part of the safety population; however, their safety data will be presented separately.

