11.5.5 Analyses of safety data

Safety analyses will be performed using the safety population by the actual treatment received, irrespective of the treatment to which the patient has been randomized. The actual treatment received is defined as:

- PAP analysis: olipudase alfa if any infusion in the PAP contains olipudase alfa (including any rescued placebo patient); placebo if all infusions in the PAP contain only placebo
- ETP analysis: olipudase alfa

Additional summaries may be conducted using the most recent dose the patient received before the event of interest.

The summary of safety results will be presented by treatment arm. All safety analyses will be performed using the following common rules:

- The baseline value is defined generally as the last available value before randomization, except hematology and ECG parameters. Baseline for hematology parameters is derived as the mean of all available results before the start of first infusion. Baseline for ECG parameters is derived as the mean of all available results on the Day 1/Week 0 visit before the start of first infusion.
- The following definitions will be applied to laboratory parameters, ECGs and vital signs.
 - The potentially clinically significant abnormality (PCSA) values are defined as abnormal values considered medically important by the sponsor according to predefined criteria/thresholds based on literature review and defined by the sponsor for clinical laboratory tests and vital signs.
 - The PCSA criteria will determine which patients had at least 1 PCSA during the on-treatment period, taking into account all evaluations performed during the on-treatment period, including unscheduled or repeated evaluations. The number of all such patients will be the numerator for the on-treatment PCSA percentage.

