#### **2.4.6 Analyses of safety data**

The summary of safety results will be presented by actual treatment received using safety population. The epochs for safety analysis have been defined in [Section 2.1.5](#). The assessment of safety measures [REDACTED] will be conducted through pooled analyses and presented in the integrated summary of safety (ISS).

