##### **2.4.6.1 Adverse events**

Pre-treatment adverse events are defined as those that have an onset date/time before the first infusion date/time of the patient. Treatment emergent adverse events are those that have an onset date/time in the treatment epoch. Any AE reported in the database with onset date after the end of the treatment epoch will be classified as post-treatment.

The epochs for safety analysis have been defined in [Section 2.1.5](#). Treatment-emergent adverse events will be presented for different periods under different treatment groups as follows (and as appropriate):

1. Adverse events started in PAP treatment epoch, by randomized treatment group.
2. Adverse events started in either PAP or in ETP while taking olipudase alfa. This will be presented by randomized treatment group as well as combined (ie, all patients treated with olipudase alfa).

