### ***Generalities***

The primary focus of adverse event reporting will be on treatment-emergent adverse events. Pretreatment adverse events will be described separately.

If an adverse event date/time of onset (occurrence, worsening, or becoming serious) is incomplete, an imputation algorithm will be used to classify the adverse event as pretreatment, or treatment-emergent. The algorithm for imputing date/time of onset will be conservative and will classify an adverse event as treatment emergent unless there is definitive information to determine it is pretreatment. Details on classification of adverse events with missing or partial onset dates are provided in [Section 2.6.2](#). If an AE worsens in severity, two AEs of same verbatim but with different start/end dates and different severity are captured separately on the AE log page in the eCRF.

The AE log page in the eCRF captures the date when the event become serious. If and when this date is non-missing, it indicates that the AE started as non-serious and became serious at a later date. To account for non-serious and serious parts of the AE collected in one AE log page, this AE will be split into two AEs – one non-serious, and one serious AE – with the same AE number, with the following modifications in data for these two AEs:

- Non-serious AE: AE end date, AE outcome, date of death or hospitalization, autopsy information, criterion for serious adverse event (SAE) will be blank.
- Serious AE: AE start date will use the date the event became serious.

Action taken towards study drug and action taken toward AE will be considered in relation to the date the event became serious, the last infusion date and dosing information, and a determination will be made, in consultation with safety monitor of the trial, as to whether the recorded fields belong to non-serious AE or serious AE; then the decision will be implemented in analysis. Any such decision will be rationalized in the CSR.

The adverse events summary will be presented by SOC and PT sorted by the internationally agreed SOC order and decreasing frequency of PTs within SOCs within the olipudase alfa treatment arm, unless otherwise specified. Multiple occurrences of the same event in the same patient will be counted only once in the tables within a particular treatment phase. The denominator for computation of percentages is the safety population within each treatment group.

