#### 2.4.6.1.1 *Treatment-emergent adverse events*

An overview of treatment-emergent adverse events (TEAEs) for PAP will be provided to include (potentially related is defined as either ‘related’ or ‘possibly related’ as assessed by the investigator):

- TEAEs
- TEAEs potentially related to study treatment
- TEAEs by severity
- TEAEs leading to treatment discontinuation
- TEAEs leading to study withdrawal
- TEAEs leading to dose reduction
- TEAEs leading to study treatment interruption
- Protocol-defined IARs
- Algorithm-defined IARs
- Treatment-emergent serious adverse events
- TEAEs with fatal outcome (deaths)
- Treatment-emergent pregnancies
- TEAEs which are considered symptomatic overdose
- Dose-limiting toxicities (collected in the adverse event log page in the eCRF, see protocol Section 8.1.6 for details)

The following summaries will be produced by primary SOC and PT:

- TEAEs
- TEAEs by severity (ie, mild, moderate, or severe)
- TEAEs potentially related to study treatment
- TEAEs potentially related to study treatment, by the worst severity (ie, mild, moderate, or severe)

The most common TEAEs are defined as those with percentages of events  $\geq 2\%$  and number of patients  $\geq 2$  in the olipudase alfa treatment group and in addition, the percentage of patients with the specific TEAEs in olipudase alfa treatment group is greater than placebo. The most common TEAEs by SOC and PT will be provided in descending order of olipudase alfa incidence, followed by placebo incidence.

Summary of TEAEs by the latest infusion dose immediately preceding the start of AE will be provided by SOC and PT.

Post-rescue PAP TEAEs by SOC and preferred term will be provided separately in a data listing using the rescue population.

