#### **2.4.6.1.5 Adverse events leading to permanent treatment discontinuation**

In this study, if the treatment is discontinued permanently, the patient is withdrawn from the study. A temporary dose interruption is not considered permanent discontinuation of study treatment. Any AEs leading to permanent treatment discontinuation will be summarized by primary SOC and PT - for PAP, ETP and cumulative over PAP and ETP. The listing of such AEs will include the olipudase alfa dose of the infusion prior to or during the occurrence of the AE leading to treatment discontinuation. Any AE leading to discontinuation of study treatment post-rescue in PAP will be provided in data listing.

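### PAP adverse-event tables have two incompatible grouping rules, and the actual-treatment rule moves a rescued placebo patient's pre-rescue events into the olipudase alfa column

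*SAP*

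**What the plan says.** **Actual treatment.** For the PAP, protocol 11.5.5 defines treatment received as "olipudase alfa if any infusion in the PAP contains olipudase alfa (including any rescued placebo patient"), and as placebo only when every PAP infusion was placebo. SAP 2.3.2 follows this: "if a placebo patient was rescued to receive olipudase alfa in PAP, this patient will be counted as olipudase alfa treated patient". SAP 2.4.6 applies it to safety in general: "The summary of safety results will be presented by actual treatment received using safety population".

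**Randomized arm.** SAP 2.4.6.1, item 1, lists the PAP adverse-event presentation as "Adverse events started in PAP treatment epoch, by randomized treatment group". The Generalities paragraph then says "The denominator for computation of percentages is the safety population within each treatment group". SAP 1.5, which lists departures from the protocol, does not mention a change of grouping.

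**Time span.** SAP 2.1.5 runs the PAP treatment epoch from the first infusion of study drug until just before the first extension-period (ETP) infusion. Rescue does not end it.

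**Post-rescue data.** SAP 2.3.2: "Data after rescue in PAP will be provided separately for the rescue population". SAP 2.4.6.1.1: "Post-rescue PAP TEAEs by SOC and preferred term will be provided separately in a data listing using the rescue population". SAP 2.4.6.1.5: "Any AE leading to discontinuation of study treatment post-rescue in PAP will be provided in data listing".

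**PAP+ETP.** For categorical measures, SAP 2.4.6.14 restricts patients randomized to placebo to their olipudase alfa time in the ETP, with baseline taken before the first ETP infusion. SAP 2.4.6.1, item 2, instead counts events in either period while on olipudase alfa. SAP 2.4.4.1 starts cumulative exposure at the first olipudase alfa dose in the study, and SAP 2.4.6.12 starts the PAP+ETP antibody baseline at the first olipudase alfa infusion.

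**The concern.** The PAP is the only randomized placebo-controlled safety comparison in the trial. With about 18 patients per arm, moving one patient between columns is visible. A patient rescued from placebo has, by definition, had a bad course on placebo. One of the three rescue triggers in protocol 8.1.6 is a clinically significant bleed attributed to low platelets, and SAP 2.4.6.1.3 makes bleeding an adverse event of interest. The event that causes rescue from placebo could therefore be tabulated under olipudase alfa, or not, depending on which section the programmer follows.

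There are three separate issues:

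- adverse-event tables have two rules;
- potentially clinically significant abnormality (PCSA), laboratory, vital-sign and ECG tables have one rule, but it attributes pre-rescue findings to a drug not yet given;
- the categorical PAP+ETP rule drops a rescued patient's PAP olipudase alfa exposure.

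**Working it through.** The plan states no figure for this point, so the check is a comparison of passages followed by an illustration.

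**Where a rescued placebo patient's PAP adverse events go**

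| Rule | Post-rescue data kept in main tables | Post-rescue data removed |
|---|---|---|
| Actual treatment | all events under olipudase alfa, including those on placebo | only placebo-period events, all under olipudase alfa |
| Randomized arm | all events under placebo, including those on olipudase alfa | placebo-period events under placebo; nothing misplaced |

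The two rules disagree in both columns, so a statement about post-rescue data alone would not settle the matter. That statement is also missing. For efficacy, SAP 2.4.5 says outright that data after rescue are not included; the safety section says only that they are shown separately.

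**Illustration**

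Inputs: 36 patients randomized 1:1 (SAP 1.4), so 18 per arm. The documents give no rescue or bleeding rate. Assume one placebo patient is rescued for a bleed, with b bleeders in the olipudase alfa arm and p other bleeders on placebo. Differences are olipudase alfa minus placebo.

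- Randomized arm: b/18 - (p+1)/18
- Actual treatment: (b+1)/19 - p/17

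| b, p | Randomized arm | Actual treatment | Shift (points) |
|---|---|---|---|
| 0, 0 | 0/18 - 1/18 = -5.6 | 1/19 - 0/17 = +5.3 | 10.8 |
| 1, 1 | -5.6 | 2/19 - 1/17 = +4.6 | 10.2 |
| 3, 3 | -5.6 | 4/19 - 3/17 = +3.4 | 9.0 |
| 6, 6 | -5.6 | 7/19 - 6/17 = +1.5 | 7.1 |
| 8, 8 | -5.6 | 9/19 - 8/17 = +0.3 | 5.9 |
| 0, 2 | 0/18 - 3/18 = -16.7 | 1/19 - 2/17 = -6.5 | 10.2 |

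With k rescued placebo bleeders and no other bleeders, the shift is k/18 + k/(18+k): 0, 10.8, 21.1 and 31.0 points for k = 0, 1, 2 and 3.

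**Most common TEAEs (SAP 2.4.6.1.1).** This table needs at least two olipudase alfa patients and a higher percentage than placebo. Take a term seen in one olipudase alfa patient, one never-rescued placebo patient, and one placebo patient before rescue. By randomized arm it is 1/18 (5.6%) versus 2/18 (11.1%), not flagged. By actual treatment it is 2/19 (10.5%) versus 1/17 (5.9%), flagged.

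**PAP+ETP.** The first ETP infusion is at Week 54. If rescue dosing began at Week 14, 26 or 38 (assumed), the categorical rule leaves out 54 - 14 = 40, 54 - 26 = 28 or 54 - 38 = 16 weeks of olipudase alfa time.

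**The case against.** The strongest defence has four parts.

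- **The actual-treatment rule is deliberate.** The protocol and SAP 2.3.2 both name rescued placebo patients. For pre-rescue events it errs against the active drug. A reader might infer that the plan hides harm from olipudase alfa; for these events the documents point the other way. The attribution is still wrong, and disclosing the rule does not remove the contrary one in SAP 2.4.6.1.
- **The contradiction is narrow.** A reader might infer from the randomized-group default in SAP 2.4 that every PAP safety table has two rules. That default is general, and SAP 2.4.6 is specific to safety. PCSA, laboratory, vital-sign and ECG tables therefore have a single rule. Likewise, SAP 2.4.6.14 departs from item 2 of SAP 2.4.6.1 only for a rescued patient; for all other placebo patients the first olipudase alfa infusion is in the ETP and the two agree. Both limits are accepted.
- **The events can be traced.** The plan has a TEAE table by last dose before onset (SAP 2.4.6.1.1), listings showing randomized arm and dose (protocol 11.5.5.1), exposure split at rescue (SAP 2.4.4.1) and narratives (SAP 2.5). This limits the chance of a wrong conclusion, but does not say which column the main tables use.
- **Rescue may be rare.** Entry excludes platelets below 60 x 10³/µL, while rescue on platelets needs a confirmed count below 30 000/mm³. This suggests, without proving, few rescues.

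**Conclusion.** The concern holds within limits. For PAP adverse events, SAP 2.3.2 and 2.4.6 cannot be reconciled with item 1 of SAP 2.4.6.1. For the other safety tables there is no contradiction, but the one stated rule puts a rescued placebo patient's pre-rescue abnormalities under olipudase alfa. Whether post-rescue data stay in the main tables is left open. For a rescued placebo patient only, the categorical PAP+ETP rule omits PAP olipudase alfa exposure and, for measures that use a baseline, takes that baseline on drug.

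One rescued placebo bleeder shifts the bleeding difference by 10.8 points if nobody else bleeds and by 5.9 points if eight others per arm do. These sizes rest on assumed counts. It would be too strong to say that the choice of rule reverses the comparison: the sign changes in the equal-count cases shown, but not with 0 olipudase alfa and 2 other placebo bleeders. The effect is zero if no placebo patient is rescued. Because SAP 2.4.6 makes the safety analysis descriptive, no formal test is affected. This should be corrected for clear safety reporting; it does not threaten the efficacy conclusions.

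**What to change.** 1. State one rule for the main PAP adverse-event and PCSA tables. Either of these keeps placebo-period events under placebo and olipudase alfa events out of the placebo column:
   - randomized arm, censored at the first rescue infusion, with the planned rescue-population output shown separately; or
   - treatment at onset, with matching denominators and a footnote that rescued patients appear in both columns.

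   In the case with no other bleeders both give -5.6 points (0/18 - 1/18, or 0/19 - 1/18).
2. Say whether post-rescue data are removed from the main safety tables, as SAP 2.4.5 does for efficacy.
3. In the categorical part of SAP 2.4.6.14, start the previous-placebo group's data and baseline at the first olipudase alfa infusion, in the PAP or ETP. The baseline for continuous longitudinal measures can stay.
4. Align protocol 11.5.5 with SAP 2.3.2, 2.4.6, 2.4.6.1 and 2.4.6.14, and record the change in SAP 1.5.

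The cost is wording and one derived flag, with no new data. The protocol's amendment history puts the PAP data cutoff at 17 October 2019, so for PAP tables already produced the regrouping should be a supplementary output, labelled as such. The rescue rule itself is unchanged.

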### **2.3.3 Other analysis populations**

The **pharmacokinetic population** consists of mITT patients who have evaluable drug concentration data.

The **pharmacodynamic population** consists of mITT patients who have at least one evaluable pharmacodynamic marker data available post-baseline.

## **2.4 STATISTICAL METHODS**

Continuous data will be summarized using the number of available data, mean, standard deviation (SD), median, minimum, and maximum for each treatment group. Categorical and ordinal data will be summarized using the number and percentage of patients. Summaries and summary plots are presented by randomized treatment group; by-patient plots and data listings will identify the randomized treatment group for each patient.

### **2.4.1 Demographics and baseline characteristics**

Parameters described in [Section 2.1.1](#) will be summarized by randomized treatment group and pooled treatment groups using descriptive statistics in mITT population.

Medical history will be summarized using body system and/or medical/surgical condition of specific interest, by randomized treatment group and pooled treatment groups in mITT population.

No specific description of the safety parameters will be provided within the baseline characteristics displays. The baseline values will be described along with each safety analysis.

No specific description of the efficacy parameters will be provided within the baseline characteristics displays. The baseline values will be described along with each efficacy analysis.

P-values on demographic and baseline characteristic data will not be provided.

